The primary goal of the phase Ib study is to assess the tolerability and safety of the combination therapy. Once the highest tolerable dose is identified or the clinical doses of imatinib (400 mg daily) and BGJ398 (125 mg qd – three weeks on and one off) are reached, the phase II portion of the study will be initiated. The primary endpoint of the phase II portion is to assess Response Rate (RR) (complete response (CR) + partial response (PR)) by RECIST 1.1.

The phase Ib portion of the study will be performed in standard 3+3 fashion. The phase Ib portion of the study will be open to all patients with locally advanced or metastatic GIST who have progressed on imatinib. An initial cohort of three eligible patients with locally advanced or metastatic GIST will initiate treatment with BGJ398 at 75 mg daily (three weeks on and one off) and imatinib at 400 mg daily for 4 weeks (1 cycle). Depending on the toxicity, dose levels of imatinib (400 mg daily) + BGJ398 will be investigated as outlined below (Table 1). As imatinib 400 mg PO QD is standard of care for metastatic GIST, this dose will remain constant (barring individual dose modifications outlined in section 9.2a).

Table 1: The dose escalation schema:

Dose Level	Imatinib	BGJ395
-2	400mg daily	25 mg qd

MEMORIAL SLOAN-KETTERING CANCER CENTER
IRB PROTOCOL

[figure not shown]
IRB#: 14-140 A (7)

-1	400 mg daily	50 mg qd
1	400 mg daily	75 mg qd
2	400 mg daily	100 mg qd
3	400 mg daily	125 mg qd

Any adverse event that meets criteria in section 9.1 that occurs prior to the second cycle (i.e. before C2D1) will be considered a Dose Limiting Toxicity (DLT) for the purposes of dose escalation to the next dose level. Any adverse event that occurs after the first cycle may require a dose reduction for the patient but will not impact the assessment of dose level safety.

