9.0 TREATMENT/INTERVENTION PLAN

Treatment will be administered on an outpatient basis. Reported adverse events and potential risks are described in Section 11. Appropriate dose modifications of imatinib and BGJ398 are described in section 9.2. No investigational or commercial agents or therapies other than those described below may be administered with the intent to treat the patient's malignancy.

MEMORIAL SLOAN-KETTERING CANCER CENTER IRB PROTOCOL

IRB#: 14-140 A (7)

Imatinib will be self administered orally by the patient on a daily basis throughout the treatment cycle. The standard treatment dose is 400 mg PO QD. 400 mg capsule will be used unless otherwise specified by the treating physician. BGJ398 will be taken at the RP2D and treatment schedule chosen from the Phase Ib portion of the trial. The RP2D selected may be lower than the MTD based on PK data and clinical tolerance beyond Cycle 1. BGJ398 is taken daily for a duration determined by the treatment schedule appropriate for the given dose level. In the event of dose delays of BGJ398, Day 1 of the following cycle will be defined as the day that BGJ398 is restarted. A pill diary for both medications will be provided and recorded (Appendix B). This will be used to assure compliance with the regimen.

On the Phase Ib portion, the timing of pharmacokinetic sample collections will be dependent on the treatment schedule onto which that patient is enrolled. For treatment schedule A pharmacokinetic samples will be drawn on Cycle 1, Day 1 at the following timepoints: 0, 1, 2, 4, 6, 8, and 24 hrs; and Cycle 1, Day 21 at the following timepoints: 0, 1, 2, 4, 6, and 8 hours. For treatment schedule B pharmacokinetic samples will be drawn on Cycle 1, Day 1 at the following timepoints: 0, 1, 2, 4, 6, 8, and 24 hrs; Cycle 1, Day 7 at the following timepoints: : 0, 1, 2, 4, 6, and 8 hours, Cycle 1, Day 15 at timepoint 0hr and Cycle 1, Day 21 at timepoint 0hr.

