**MEMORIAL SLOAN-KETTERING CANCER CENTER
IRB PROTOCOL**

IRB#: 14-140 A (7)

The first three patients will be enrolled at Dose level 1 (Table 1, see section 1) using treatment schedule A. Dose level 1 is chosen based on the standard of care imatinib dose of 400 mg daily in the advanced GIST patient population, and an intermediate dose level of BGJ398 (75 mg daily). This dose is below the BGJ398 MTD of 125 mg daily identified in phase I trials as monotherapy. BGJ398 dose level 1 to -2 will be administered using a schedule of BGJ398 taken daily for 3 weeks followed by one week off and imatinib taken daily throughout the 4 week cycle period (treatment schedule A).

The maximum pace of dose escalation within each cohort is outlined in Table 2. Expansions of lower dose levels may be made based on safety and tolerance considerations at the MSKCC Principal Investigator's discretion, and the selected RP2D may be lower than the MTD defined below. If dose level 1 is not found to be tolerable, then the next cohort will be enrolled at dose level -1. If dose level -1 is not found to be tolerable, then the next cohort will be enrolled at dose level -2. If dose level -2 is not found to be tolerable, then the study may be terminated based on discussions with the MSKCC Principal Investigator. If 0-1 of 6 patients experience a DLT on dose level 3, this will be the RP2D.

Table 2:

Number of Patients with DLT at a Given Dose Level	Escalation Decision Rule
0 out of 3	Enter 3 patients at the next dose level.
1 out of 3	Enter at least 3 more patients at this dose level. 
 • If 0 of these additional 3 patients experience DLT (1/6 total), proceed to the next dose level. • If 1 or more of this group suffer DLT ($\geq 2/6$ total), then dose escalation is stopped, and this dose is declared the MTD. Three (3) additional patients will be entered at the next lowest dose level if only 3 patients were treated previously at that dose.
≥ 2	Dose escalation will be stopped. This dose level will be declared the MTD. Three (3) additional patients will be entered at the next lowest dose level if only 3 patients were treated previously at that dose.
≤ 1 out of 6 at highest dose level below the MTD	This is generally the recommended phase 2 dose. At least 6 patients must be entered at the recommended phase 2 dose (RP2D).

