Following resolution of toxicity to baseline or \leq grade 1, treatment is resumed at either the same or lower doses of study drugs as per the criteria in Table 6. If treatment is resumed at the same doses of study drugs, and the same toxicity recurs with the same or worse severity regardless of duration, doses must be reduced to the next lower dose level (Table 6). If treatment is resumed at the lower doses of study drugs, and the same toxicity recurs with the same or worse severity, the patient must discontinue study treatment unless a continuation is allowed in discussion with the MSKCC PI.

If a patient requires a dose delay of > 14 consecutive days of BGJ398 from the intended day of the next scheduled dose, then the patient should be discontinued from the study treatment unless a continuation is allowed in discussion with the MSKCC PI.

In exceptional situations, study treatment may continue even if the patient experienced one of the treatment stopping rules. The decision to allow for continuation of treatment will be made on a case-by-case basis following discussion between the MSKCC Principal Investigator (MPI) and the Investigator. Situations that may allow for continuation of treatment include but are not limited to the following. A dose delay of > 14 days has occurred, but the patient is clearly benefiting from study treatment (i.e., stable disease, partial response, or complete response) and it is the investigator's opinion that no safety concerns are present, after discussion with the MPI, the patient may remain on the study treatment. A third or subsequent reduction (to dose level -3) in dose may be allowed if the patient is clearly benefiting from study treatment (i.e., stable disease, partial response, or complete response) but is experiencing adverse events that prevent continued treatment at the already reduced dose.

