Fatigue Grade 3	Hold dose of BGJ398 until resolved to CTCAE Grade ≤ 1 
 • If resolved in ≤ 7 days, maintain dose level of BGJ398. • If resolved in > 7 days, discontinue patient from study treatment.
Other clinically significant AEs	
Grade 3	Hold dose of BGJ398 until resolved to CTCAE Grade ≤ 1, then ↓ 1 dose level of BGJ398.
Grade 4	Discontinue patient from study treatment.
All dose modifications should be based on the worst preceding toxicity. Once a dose has been reduced it will not be increased at a later time even if there is no toxicity. Patients who require more than two dose reductions of BGJ398 will be discontinued from study drug treatment. If a patient requires a dose delay of > 14 days from the intended day of the next scheduled dose of BGJ398 then study treatment must be stopped.	

Table 8: Prophylaxis and Treatment recommendations for hyperphosphatemia without kidney injury:

Hyperphosphatemia Prophylaxis (Patients receiving treatment schedule A)	Initiate Sevelamer 800 mg with meals (up to TID) concurrent with BGJ398, unless otherwise contraindicated by patient's current medical condition. Restrict dietary phosphate intake to 600 – 800 mg/day, if BMI ≥ 21kg/m ² .
Hyperphosphatemia Treatment Without Elevated Creatinine	INTERVENTION
Serum Pi > 5.5 – 7.0mg/dL:	Continue sevelamer 800 mg with 2 meals per day and increase the dose of sevelamer with the largest meal to 1600mg (total daily dose = 3200 mg).
Serum Pi 7.1mg – 9.0mg/dL	Increase the dose of sevelamer up to 1600mg (2 tablets per meal) every 8 hours and continue sevelamer through Day 21 and until Serum Pi is <5.5, whichever is later. Sevelamer should be given even on days BGJ398 is not taken until serum Pi is <5.5. If serum Pi ≤ 7.0 mg/dL within 7 days, increase sevelamer to 1600 mg TID with next cycle, if not already done so. No interruption or adjustment to BGJ398 is necessary. If Serum Pi >7.0 mg/dL for longer than 7 days, hold BGJ398 until serum Pi is <5.5 mg/dL. Assess if patients were taking Sevelamer 1600 mg TID on Day 1 of most recent cycle.

MEMORIAL SLOAN-KETTERING CANCER CENTER
IRB PROTOCOL

IRB#: 14-140 A (7)

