14.0 BIOSTATISTICS

This is a multi institution single arm phase Ib/II trial to evaluate the clinical safety and efficacy of imatinib and BGJ398 in patients with advanced Gastrointestinal Stromal Tumors. Patients in the Phase Ib portion of the trial are required to have metastatic and or locally advanced GIST that has been treated with imatinib. Patients on the Phase II portion of the study are required to have advanced GIST and not have received any prior systemic therapy (untreated/treatment naïve).

Phase 1b Portion Study Design and Endpoint Assessment

The primary endpoint of the phase 1b portion of this study is to determine the maximum tolerated dose (MTD) and treatment schedule of BGJ398 administered in combination with imatinib in patients with GIST. The phase 1b will be pursued in standard 3+3 format, based on toxicities encountered during the first cycle of therapy.

The dose escalation schema is listed in Table 1. Dose escalation will proceed within each cohort according to Table 2. The first three patients will be enrolled at Dose Level 1. If dose level 1 is not found to be tolerable, then the next cohort will be enrolled at dose level -1. If dose level -1 is not found to be tolerable, then the next cohort will be enrolled at dose level -2. If dose level -2 is not found to be tolerable, then the study may be terminated based on discussions with the MSKCC Principal Investigator. If 0 or 1 of 6 patients experience a DLT on dose level 3, this will be the RP2D unless a lower dose is selected based on chronic tolerance of the combination and pharmacokinetic data. Lower dose levels may be expanded and an RP2D lower than the MTD may be selected based on safety and chronic tolerance considerations by the MSKCC Principal Investigator. If dose level 1 to -2 is identified as the MTD and concern exists regarding therapeutic activity of BGJ398 at this dose level, expansions with higher dose levels (1 to 3) may be considered at the MSKCC PI's discretion, with modification of the treatment schedule. When the RP2D is found, any patients from the Phase Ib portion of the study who remain on therapy below the MTD may have their BGJ398 dose increased to the MTD at the treating physician's discretion.

MEMORIAL SLOAN-KETTERING CANCER CENTER IRB PROTOCOL

IRB#: 14-140 A (7)

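### Section 14 caps optional phase Ib dose increases at the MTD instead of the RP2D, so it can allow a BGJ398 dose above the one chosen for phase II

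*Combined protocol and SAP*

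**What the plan says.** The permission is in Section 14.0, in the phase Ib design text. Once the RP2D is found, any phase Ib patients "who remain on therapy below the MTD may have their BGJ398 dose increased to the MTD at the treating physician's discretion". The increase is optional. The only control named is the treating physician's judgement, and the only condition is being on therapy below the MTD.

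Four other places bear on it:

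- **Table 2 (Section 9.1), MTD.** If 1 of the first 3 patients has a DLT and the expanded cohort reaches at least 2 of 6, "then dose escalation is stopped, and this dose is declared the MTD". The row for 2 or more DLTs uses the same label.
- **Table 2, RP2D.** Of the highest level below the MTD with at most 1 of 6 DLTs, the table says: "This is generally the recommended phase 2 dose".
- **Section 9.0.** "The RP2D selected may be lower than the MTD based on PK data and clinical tolerance beyond Cycle 1". Sections 9.1 and 14 also allow an RP2D below the MTD.
- **Table 7 closing note (Section 9.3.2).** "Once a dose has been reduced it will not be increased at a later time even if there is no toxicity". Section 9.3.2 is not limited to phase II, and Section 1.0 foresees reductions in phase Ib: "Any adverse event that occurs after the first cycle may require a dose reduction for the patient".

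**The concern.** The RP2D is the dose the investigators judge fit for continued use, after weighing cycle 1 DLTs, pharmacokinetics and later tolerance. Finding it is what triggers the option to increase. The natural ceiling for that option is therefore the RP2D itself, but the sentence names another dose, one that the protocol defines in two ways.

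A patient who is stable on a lower dose could be raised above the dose just selected. On the Table 2 definition, the target is a level that has just failed the escalation rule. The patients concerned have stayed on treatment longest, so an RP2D lowered for chronic tolerance matters most to them. The control is also light: Section 9.3.2 requires discussion with the MSKCC Principal Investigator before treatment continues past a stopping rule, whereas this increase needs only the treating physician.

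The sentence is also silent on patients who are below the MTD because BGJ398 was reduced for toxicity.

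**Working it through.** The plan gives no figure for this provision, so there is nothing to reproduce. The check sets the rules side by side and sizes the gap.

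**1. Can the target exceed the RP2D?**

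| Meaning of MTD | Target in Section 14 | RP2D | Above the RP2D? |
|---|---|---|---|
| Table 2: level that stopped escalation (at least 2 DLTs) | That level | Generally one level lower | Yes |
| Usual: highest tolerated level, RP2D set equal to it | That level | Same level | No |
| Usual, RP2D lowered for PK or later tolerance | That level | Lower | Yes |
| Level 3 cleared (0–1 of 6 DLTs) | Table 2 declares no MTD; presumably 125 mg | 125 mg, or lower under Section 14 | Only if the RP2D is lowered |

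No single meaning keeps the target at or below the RP2D in every case.

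**2. Size of the dose gap.** Table 1 levels are 25, 50, 75, 100 and 125 mg. With the RP2D one level below the MTD, the step is 25 mg:

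- 125/100 = 1.25
- 100/75 = 1.33
- 75/50 = 1.50
- 50/25 = 2.00

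**3. Observed DLT rates implied by Table 2 (exact 95% intervals).**

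- Level called the MTD, after expansion: at least 2/6 = 33% (for 2/6: 4% to 78%).
- Level called the MTD, without expansion: at least 2/3 = 67% (for 2/3: 9% to 99%).
- Level generally taken as the RP2D: at most 1/6 = 17% (for 1/6: 0.4% to 64%).

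These rates are imprecise. Under Table 2, a level with true DLT rate p stops escalation with probability 1 − [(1−p)³ + 3p(1−p)⁵]. For assumed rates of 0.10, 0.20, 0.30, 0.40 and 0.50 this is 9%, 29%, 51%, 69% and 83%. A stopped level is thus a warning, not proof of a high DLT rate.

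**4. Reduced patients.** Take a patient enrolled at 100 mg and reduced after cycle 1, with 125 mg labelled the MTD. Section 14 alone would permit 125/100 = 1.25 times the dose at which the toxicity occurred, whatever the reduction step. Table 7 permits no increase. Section 14 is permissive and Table 7 is a prohibition, so a physician who follows both leaves the dose where it is. The exceptions in Section 9.3.2 cover continuation, delay and further reduction, not an increase. The encouragement to re-escalate in Section 9.3.1 sits under the imatinib heading.

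**5. Conditions a repair must meet.**

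- Excluding reduced patients is not enough. ALT of grade 3 or higher is a DLT in Table 3, yet Table 7 keeps the dose if a grade 3 rise (without bilirubin above 2 × ULN) resolves within 7 days. A patient can have a DLT and no reduction.
- Dose alone does not rank the two schedules. Schedule A at 75 mg gives 75 × 21 = 1,575 mg per cycle. Schedule B at 125 mg gives 125 × 7 = 875 mg, which is 44% less (1 − 875/1,575), although the daily dose is higher.

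**The case against.** The strongest reply is that Section 14 means the MTD in its usual sense. The same paragraph considers level 1 down to −2 being the MTD and asks whether BGJ398 would be active enough there. That question makes sense only for a dose one might keep using. Allowing an RP2D below the MTD is likewise an extra option only if the MTD is tolerated. Section 1.0 speaks of the highest tolerable dose, and the monotherapy MTD of 125 mg lay below a 150 mg level with two DLTs. This stands: a reader might infer that the plan intends to raise patients to a level known to be too toxic, and the documents do not support that. The fault lies partly in the Table 2 label. But Section 9.1 points to the MTD as defined in that table, so a site can reasonably apply it. The usual sense also does not remove the problem when the RP2D is lowered for tolerance.

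A reader might also infer that Section 14 and Table 7 contradict each other. They do not, because a discretionary permission gives way to a specific prohibition without breach of either.

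It can fairly be added that the DLT intervals overlap almost completely, that cycle 1 rates at a starting dose do not give the risk for someone already tolerating a lower dose, and that going modestly above an RP2D lowered for tolerance, to a level with at most 1 of 6 DLTs, is debatable, not plainly unsafe. These points limit the size of the concern. They do not explain why the ceiling should differ from the dose whose selection triggers the option.

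**Conclusion.** The concern holds in a limited form. The ceiling for optional phase Ib increases is set at the MTD, and under either meaning of that term the sentence can allow BGJ398 above the RP2D. With the RP2D one level below, the excess is 25 mg, or 1.25 to 2.0 times. The missing link to Table 7 is a needed cross-reference, not a conflict of rules.

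This is a low-to-moderate patient-safety correction. It assumes that a physician uses the option, and either that Table 2's label is applied or that the RP2D is set below a tolerated MTD. The number of patients affected is not given; it is probably a small part of the 6 to 30 planned for phase Ib, since only those still on therapy when the RP2D is found qualify.

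A reader might infer that the RP2D or the phase II result is compromised. Neither is: the increase comes after the RP2D is chosen, DLTs are counted in cycle 1 only, and Section 14 keeps phase Ib patients out of the final efficacy analysis.

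**What to change.** 1. Replace the Section 14 sentence with: *Once the RP2D has been set, a phase Ib patient still on therapy at a BGJ398 dose below the RP2D on the same treatment schedule, who has had no DLT and no BGJ398 dose reduction for toxicity (see Table 7), may be increased up to, but not above, the RP2D if the treating physician judges it appropriate.*
2. Correct Table 2 so that a level with at least 2 DLTs is described as exceeding the MTD, and the MTD is the highest level with at most 1 of 6 DLTs. Reword the RP2D row to match. The passages in Sections 9.1 and 14 on a low MTD, and on an RP2D below the MTD, then read consistently. Schedule B uses the same table, so the correction carries over.

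The cost is one sentence and a few table entries, with no extra patients, visits, data or analyses. The same-schedule condition means that a schedule A patient would not be increased under this rule if the RP2D is on schedule B. That is acceptable, because a dose on one schedule cannot simply be called higher or lower than a dose on the other.
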